11. CONFIDENTIALITY OF DATA AND DATA STORAGE

11.1 Data Collection Table

FORM	Baseline	Post Intervention
On Study Data (Demographic and clinical data)	X	
Clinical Record Information (Clinical data – survivor only)	X	
Medication Form	X	
Physical Activity Readiness Questionnaire (PAR-Q+)	X	
Profile of Mood States (POMS)	X	X
Aerobic Center Longitudinal Study Physical Activity Questionnaire (ACLS; 15-item physical activity history measure)	X	X
Patient Health Questionnaire - 9 (PHQ-9)	X	X
Spielberger State/Trait Anxiety Inventory (STAI Form Y-1)	X	X
Short Form Health Survey 12 (SF-12)	X	X
Dyadic Adjustment Scale – 7 (DAS-7)	X	X
Dyadic Support Questionnaire (DSQ)	X	X
PROMIS Patient-Reported Item Batteries	X	X
Insomnia Severity Index (ISI)	X	X
Multidimensional Fatigue Symptom Inventory (MFSI)	X	X
Heterosexism and Identity Questionnaire	X	X
Physician Interaction (PEPPI, THC, and SSE) Scales	X	X
Physiological Fitness Test Evaluations (6 min walk test, handgrip dynamometry, isokinetic strength test, bioelectrical impedance)	X	X
Heart Rate Variability (Firstbeat Bodyguard 2)	X	X
Biological Endpoints (via blood draw)	X	X
Pedometer (or fitness tracker)	Continuous (for those exercising)	Continuous (for those exercising)
Actigraphy	7 days before	7 days before
Daily Diary	Continuous (for those exercising)	Continuous (for those exercising)

- 11.2 All hardcopy research records will be stored onsite in the University of Rochester Medical Center, in the Cancer Control Unit and the PEAK Lab of the James P. Wilmot Cancer Institute. The Cancer Control Unit is located in the Saunders Research Building, in an office suite secured by electronic key cards. The PEAK Lab is located in the medical center and is also secured by electronic key cards. Offices within the Unit and the Lab are again secured by key and data is kept in locked file cabinets. Electronic research records are stored on the University of Rochester Medical Center's password secured and

Protocol date: 7/06/2020

firewall protected networks. These are the same methods of security used for patient medical records. Human serum samples are stored in locked freezers, within locked and alarmed laboratories that are accessible by key codes and electronic card swipes. All study data will be kept for a period of at least 6 years after the study and all reports and publications are complete.

- 11.3 All data (information and human blood samples) collected for the current study will be used in post hoc analyses as appropriate. Blood samples will be banked and data will be used for future studies only with prior consent of participants (cancer survivors and caregivers). The consent form contains appropriate language related to biobanking and participants are given the option to have their samples banked or to have them destroyed following analysis of the study hypotheses. Participants' individual research records will not be shared with their treating physician, unless they provide consent or the patient's treating physician is a study physician, in which case they will have access to study data as a study co-investigator. Overall study results will be presented to participants, faculty and staff at the University of Rochester Medical Center after completion of the study. Study results will be presented at professional meetings and published.
- 11.4 The study team will assign a numerical Study ID to each participant once they have signed the consent form. Study forms and questionnaires will use this number and the participant's first and last initials as identifiers to ensure data integrity. Other identifying information will not exist on these forms. A complete list of study participants with study ID, name, and contact information will be maintained separately for the purpose of contacting participants for weekly phone call or e-mail reminders; this database will be maintained until the study is closed. This linkage information will only be accessible to the study chair, study investigators, and the individual responsible for maintaining the database.

12. RESEARCH INFORMATION IN MEDICAL RECORDS

- 12.1 Documentation of study participation will be included in the medical record by means of uploading a signed consent form to each cancer survivor's medical record, for those participants enrolled in the research study from Wilmot Cancer Institute/University of Rochester Medical Center. Participants' blood draw at the Clinical Research Center will also be noted in the medical record as an outpatient appointment. No further research-related information will be included in the medical record.

13. DATA ANALYSIS AND DATA MONITORING

13.1 Measures for the primary and secondary aims will be:

- 13.1.1 Cancer survivor's self-reported psychological distress (30 item POMS Total Score) at post-intervention (Primary Aim 1)
- 13.1.2 Cancer survivor's serum levels of stress-related biological endpoints (cortisol, serum amyloid A, C-reactive protein) at post-intervention (Secondary Aim 2)
- 13.1.3 Cancer survivor's received support from the caregiver (Dyadic Support Questionnaire) at post-intervention (Secondary Aim 3)
- 13.1.4 Cancer survivor's physical activity, as measured by actigraphy, at post-intervention (Secondary Aim 3)

13.2 Measures for the exploratory aim in caregivers will be:

- 13.2.1 Caregiver's self-reported psychological distress (30 item POMS Total Score) at post-intervention
- 13.2.2 Caregiver's serum levels of stress-related biological endpoints (cortisol, serum amyloid A, C-reactive protein) at post-intervention
- 13.2.3 Caregiver's received support from the cancer survivor (Dyadic Support Questionnaire) at post-intervention
- 13.2.4 Caregiver's physical activity, as measured by actigraphy, at post-intervention

13.3 Data Analysis

- 13.3.1 The primary outcome measure for this study is the cancer survivor's self-reported psychological distress, as assessed by the 30 item Profile of Mood States (POMS) Total score at the post-intervention time point (~6 weeks after baseline). The primary analyses will involve a comparison of EXCAP-PA relative to survivor-only EXCAP[®] using analysis of covariance (ANCOVA). This procedure assesses the statistical significance of the difference in post-intervention mean between the two arms, controlling for baseline score and using intent to treat analyses with 30 evaluable survivors per arm. The comparison of EXCAP-PA to survivor-only EXCAP[®] assumes a null hypothesis of no difference, using a two-sided alpha. We will use ordinary least-squares estimation and F-tests for testing the fixed effects. Primary aim analyses will treat the LGBT cancer survivor as the unit of analysis. The mean difference between groups with associated 95% confidence intervals will be estimated using the appropriate contrasts. This study will establish initial efficacy of the dyadic intervention and provide an initial effect size for the intervention that will inform the development of a larger Phase III trial.
- 13.3.2 Secondary analyses will use standardized procedures developed by [name] and the Rochester Human Immunology Core to measure serum levels of distress-related biological endpoints (serum amyloid A, CRP, cortisol) via ELISAs. The efficacy of EXCAP-PA relative to survivor-only EXCAP[®] in improving markers of HPA axis functioning (cortisol) and early

inflammation (SAA, CRP) will be assessed using three separate ANCOVAs, each controlling for baseline biological marker values, and two ANCOVAs for dyadic support and intervention adherence. Since the secondary aims, relating to immune biomarkers of distress and provision of support within the dyad, are intended to gather preliminary efficacy data for the development of a larger grant submission, the secondary analyses will also examine mean change scores (i.e., baseline assessment subtracted from the post-intervention assessment), standard deviations, and correlations on these variables for the two study arms.

13.3.3 The current study is neither structured nor powered to permit true analysis of mediation.

However, exploratory analyses will involve examining associations between outcomes of interest (distress and biological endpoints) and potential mechanistic factors (social support from a caregiver, adherence to the exercise intervention). Using the analysis techniques of Imai, I will evaluate whether change in social support and change in intervention adherence are associated with the effect of the intervention on psychological distress and biological endpoints linked with distress. This will involve generating a correlation matrix to test bivariate relationships. We will then conduct separate analyses for support and adherence with each outcome, using mixed effects ANCOVA models with arm, baseline distress or biomarker score, with/without support and adherence pre-post change scores as model predictor terms. We will also evaluate change in caregiver distress scores from baseline to post-intervention in the EXCAP-PA condition using paired sample t-tests, to examine whether caregivers benefit from supporting LGBT cancer survivors. We will also examine outcomes in L, G, B, and T subgroups and evaluate confounding and moderating factors. Because of the many exploratory analyses involved, any results will only be used for hypothesis generation.

13.3.3 Additional analyses will examine between group differences in the other outcome measures.

These will include: physical activity (ACLS, Daily Diaries), aerobic capacity (6 minute walk test), muscular strength (handgrip dynamometry, isokinetic strength test), depression (CES-D), anxiety (STAI), minority stress (Heterosexism and Identity Scale), relationship satisfaction (DAS-7), and quality of life (SF-12).

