2.3 Secondary Aims (in survivors)

- 2.3.1 To determine the preliminary effect of EXCAP-PA versus survivor-only EXCAP[®] on biological endpoints associated with distress: markers of HPA axis functioning (cortisol) and markers of early inflammation (serum amyloid A [SAA], C-reactive protein [CRP])
- 2.3.2. To determine the preliminary effect of EXCAP-PA versus survivor-only EXCAP[®] on social support from the caregiver (Dyadic Support Questionnaire [DSQ]) and intervention adherence (actigraphy).

2.4 Exploratory Aims (in survivors):

- 2.4.1 To explore preliminary mechanistic relationships between self-reported distress, markers of HPA axis functioning and early inflammation, social support from the caregiver, and intervention adherence.

2.5 Exploratory Aims (in caregivers):

- 2.5.1 To determine the preliminary effect of EXCAP-PA versus survivor-only EXCAP[®] on self-reported psychological distress and biological endpoints associated with distress among caregivers.

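### The exploratory mechanism models enter the change in support or activity without that variable's own baseline, so the change coefficient may be unbiased, attenuated or reversed in sign, depending on relations the documents do not give

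*Combined protocol and SAP*

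**What the plan says.** Aim 2.4.1 is "To explore preliminary mechanistic relationships between self-reported distress, markers of HPA axis functioning and early inflammation", together with caregiver support and adherence. The analysis is in the first of the two paragraphs numbered 13.3.3. After a correlation matrix, the plan says: "We will then conduct separate analyses for support and adherence with each outcome". The models are "mixed effects ANCOVA models with arm, baseline distress or biomarker score, with/without support and adherence pre-post change scores as model predictor terms". Section 13.3.2 defines change as "baseline assessment subtracted from the post-intervention assessment".

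The same paragraph adds a general intention to "evaluate confounding and moderating factors" and refers to Imai's techniques, but it names no covariates for either. It limits the use of the results: "Because of the many exploratory analyses involved, any results will only be used for hypothesis generation". It also opens with a disclaimer: "The current study is neither structured nor powered to permit true analysis of mediation".

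Both missing baselines exist. The table in 11.1 has the DSQ at baseline and post-intervention, and 10.2.1.3 sets actigraphy windows before day 0 and before day 42.

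**The concern.** A model that contains the change M1 − M0 but not M0 assumes that baseline and post-intervention support have equal and opposite effects on post-intervention distress. A change score is also negatively correlated with its own baseline: survivors who start with good support have less room to gain. If good starting support itself goes with lower distress later, part of that benefit enters the change coefficient with its sign reversed.

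Aim 2.4.1 is answered by these coefficients and the correlation matrix. Hypothesis generation is their stated purpose, and 13.3.1 and 13.3.2 look ahead to a Phase III trial and a larger grant submission. A coefficient that is too small, or has the wrong sign, would weaken the hypotheses carried forward.

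**Working it through.** **The plan's own figure.** The documents give no power or effect size for the mechanism models. Their only power figure is for the primary comparison: 80% for a POMS difference of 6.90 with SD 13.01 and correlation 0.7 (13.5.1) and 30 evaluable survivors per arm (13.3.1). The ANCOVA residual SD is 13.01 × √(1 − 0.7²) = 9.29. The two-sided t calculation on 57 degrees of freedom gives 80.7%, so the figure reproduces. The number of survivors (60) and the correlation (0.7) are carried forward.

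**Population algebra.** Let distress be Y and support M, with M0 and M1 of equal variance, and let

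Y1 = b·Y0 + c1·M1 + c0·M0 + error.

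Because c1·M1 + c0·M0 = c1·(M1 − M0) + (c1 + c0)·M0, leaving out M0 moves part of (c1 + c0) into the change coefficient. Let r be the baseline support-distress correlation, ρ the stability of support, and k = c0/c1. If M1 depends on Y0 only through M0, the planned coefficient as a share of c1 is

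share = 1 − (1 + k)(1 − r²) / (2 − (1 − ρ)r²).

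With r = 0 this is (1 − k)/2, so the planned coefficient is (c1 − c0)/2 whatever the stability. With M0 in the model the coefficient is c1 in every case.

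Worked example with k = 0, r = −0.3, ρ = 0.74: 1 − 0.91/(2 − 0.26 × 0.09) = 1 − 0.91/1.9766 = 0.54. A true −0.30 then appears as −0.16.

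**Range.** The assumed values are r from 0 to −0.5 and ρ of 0.5, 0.74 and 0.92. The last two are the DSQ test-retest limits in 10.1.5.2. Test-retest reliability is not the same as six-week stability, but it is the only such figure in the documents.

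| How baseline support acts | k | Share of c1 recovered |
|---|---|---|
| Change drives change | −1 | 100% |
| Concurrent effect at each visit (r = −0.3 or −0.5; distress correlation 0.7) | −0.63 to −0.77 | 85% to 91% |
| Only post support matters | 0 | 50% to 62% |
| Baseline has half the post effect | 0.5 | 25% to 43% |
| Equal effects | 1 | 0% to 24% |
| Baseline has 1.5 times the post effect | 1.5 | −25% to 5% |
| Baseline has twice the post effect | 2 | −50% to −14% |

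The share reaches zero at k = (1 + ρr²)/(1 − r²). That is 1.0 at r = 0, 1.17 at r = −0.3 with ρ = 0.74, and 1.64 at r = −0.5 with ρ = 0.92. The sign reverses only above that value.

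**Simulation.** 60 survivors, 30 per arm, 4,000 runs per cell, arm in the model. Y1 = 0.7·Y0 + c1·M1 + c0·M0 + error with error SD √(1 − 0.7²) = 0.71. Support is in SD units and r = −0.4 (assumed).

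- Only post support acts (c1 = −0.30): the planned slope averages −0.17. Power at stability 0.6, 0.7 and 0.8 is about 30%, 25% and 19% as planned, against 68%, 60% and 47% with baseline support added. At 0.74 it is 22% against 55%, and at 0.92 it is 10% against 22%.
- Only baseline support acts (c1 = 0; c0 = −0.2 or −0.3): at stability 0.7 the planned model rejects 10% or 16% of the time at the 5% level, almost always in the direction of more support with more distress. At 0.74 the rates are 9% and 14%, and at 0.92 they are 6 to 8%. With baseline added the rate is about 5%.
- Change drives change (c1 = −0.30, c0 = +0.30, stability 0.7): both models are unbiased. Power is about 65% as planned and 59% with baseline added.

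**The case against.** The size of the problem depends on a structure that the documents do not specify. If support acts on distress concurrently at both visits, the planned slope averages about −0.26 against −0.30, and power at stability 0.6, 0.7 and 0.8 is 71%, 56% and 41% against 75%, 63% and 47%. That is a loss of 4 to 7 points. If change drives change, the planned model is right and slightly more powerful. The question in 13.3.3 is worded in terms of change, so leaving out the baseline could be read as a choice of estimand. The results are labelled hypothesis-generating, mediation is disclaimed, and a correlation matrix will also be produced.

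Most of this stands, and it limits the point to an inexpensive improvement of an exploratory analysis. It does not remove the point. The plan gives no reason to assume the one structure in which the coefficient is unbiased. The general intention about confounders names no variable and is not attached to these models. Generating hypotheses is also the task that a distorted coefficient harms.

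A reader might infer that regression to the mean will hide a real link, or that most of the signal is lost. The documents do not support that: the loss runs from nil upwards, and where only post support matters just over half of the slope remains in most settings. A reader might also infer that rising support will generally look harmful. That requires baseline support to protect more than post-intervention support. Unreliable measurement alone does not produce it: if support is a stable trait measured with noise, the planned coefficient is zero, not reversed.

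**Conclusion.** The point holds in a conditional form. The listed terms omit the mechanism variable's own baseline. The change coefficient may therefore be unbiased, reduced by about 9 to 15%, roughly halved, or reversed, according to how baseline support relates to later distress. All of these sizes rest on assumed support-distress relations, equal variances at the two visits and a linear model. The documents supply only the POMS correlation of 0.7, the sample size and the DSQ test-retest range. The figures were worked for support; the same algebra applies to actigraphy.

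The effect is confined to exploratory aim 2.4.1. The primary ANCOVA in 13.3.1 and the secondary ANCOVAs in 13.3.2 do not use these terms.

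The mixed-effects label might also be taken as a substantive error. Each survivor has one post-intervention value per outcome and no random effect is named, so the label does not fit a survivor-level model. No estimate has been shown to change because of it.

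**What to change.** In the mechanism paragraph of 13.3.3, state that every model containing change in support also includes the survivor's baseline DSQ received-support score (the scale named in 13.1.3), and that every model containing change in activity also includes baseline actigraphy. State that these models are fitted by ordinary least squares, as in 13.3.1, which also settles the mixed-effects wording.

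The cost is one sentence of text and one degree of freedom per model, with no new data. If only change matters, power falls slightly (about 65% to 59% in the simulation above). In exchange, under the linear model used here, the coefficient no longer depends on how baseline support relates to later distress.

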4. PARTICIPANT IDENTIFICATION, RECRUITMENT AND CONSENT

4.1 Human Subjects Involvement: The proposed RCT aims to recruit 70 lesbian, gay, bisexual, and transgender (LGBT) cancer survivors who have completed treatment (surgery, radiation, or chemotherapy) or who are on continued, indefinite adjuvant treatment, so as to have a final, evaluable sample of 60 LGBT survivors after attrition. The proposed RCT will also recruit caregivers (broadly defined) of the above cancer survivors. Each recruited cancer survivor will be asked to name a person who they feel provided care (emotional, informational, tangible, etc.) during their cancer experience, with no further strictures placed on this relationship in terms of type or duration. The caregiver will be approached to participate in the RCT. Thus the sample will consist of 70 LGBT survivors (60 evaluable) and their caregivers (140 individuals total/120 evaluable). Recruitment and primary analyses will specifically target the LGBT cancer survivor.

LGBT survivors will be randomized to one of 2 arms: Arm 1, a novel, *partner-assisted*, LGBT-specific framework incorporating EXCAP[®] (Exercise for Cancer Patients, a standardized, daily, 6 week, progressive walking and resistance training program), in which both survivors and caregivers will receive EXCAP[®] materials and be instructed in their use together, or Arm 2, a *survivor-only* version of EXCAP[®], in which only the cancer survivor will receive EXCAP[®] materials and be instructed in their use. There will be 35 LGBT survivors randomized to each arm (30 evaluable), along with their 35 caregivers (30 evaluable). Survivors and caregivers will be assessed before and after the 6 week intervention in both arms. The LGBT survivor will be the primary unit of analysis; data collected from caregivers will be used for exploratory purposes only.

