The study chair, study coordinator, and Certified Exercise PhysiologistSM have received appropriate training, as well as password secured access to use the University of Rochester Medical Center's electronic patient scheduling and clinical information systems to obtain medical information and appropriate source documentation for research files.

- 6.3.3 During the consent meeting, all participants will be given a pedometer (or a fitness tracker such as the FitBit) and an Actigraph to wear for approximately 4-7 consecutive days before the baseline assessment. The pedometer (or fitness tracker) and actigraph will be collected at the baseline assessment and returned to all participants for approximately 4-7 days of monitoring prior to the post-intervention assessment.
- 6.3.4 The study team member will schedule a time for survivor and caregiver to return to the PEAK Lab to complete the baseline assessment. The study team member will make phone or e-mail contact with survivor and caregiver approximately 7 days before their scheduled baseline assessment to remind them to wear their pedometers (or fitness trackers) and actigraphs.

6.4 *Baseline assessment*

- 6.4.1 **All assessments will be done on all study participants (cancer survivors and their caregivers).** Survivors and caregivers can complete assessments either as a dyad or individually. The sequence of assessments will be the same at baseline and post-intervention.
- 6.4.2 **Blood draw.** At the baseline assessment (and again at the post-intervention assessment), blood sampling will be done to estimate hematocrit, hemoglobin, lymphocytes, monocytes, and biological endpoints of interest (serum amyloid A, CRP, cortisol, along with mRNA concentrations of these endpoints). Blood draws can be conducted with cancer survivor and caregiver together or separately, on the same day as the baseline assessment or up to a week before the baseline assessment. The consent form will include a section asking whether participants agree to have their samples biobanked for additional, future analyses. Participants will have the option to check yes or no to having their samples biobanked.

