6.5.2.3 Participants will be instructed in the proper methods for performing each exercise by an ACSM Certified Exercise PhysiologistSM. For those randomized to the dyadic intervention, this will involve a 45-60 minute meeting between the Physiologist and both the survivor and the caregiver. For those randomized to the individual intervention, this will involve a 45-60 minute meeting between the Physiologist and the survivor alone.

6.6 ***EXCAP-PA:*** Partner-Assisted Home-Based Walking and Progressive Resistance Exercise Program

6.6.1 Those randomized to Arm 1, the Partner-Assisted version of EXCAP, will receive the EXCAP program instruction as a dyad, as described above. After the Physiologist has demonstrated proper methods for performing each exercise to the dyad, a trained member of the study team will meet with participants. This meeting will involve a discussion of barriers that might reduce adherence to the intervention for each participant, ways that cancer survivor and caregiver can support one another in remaining adherent, and ways of dealing with stress (including LGBT minority stress). Those randomized to Arm 2, survivor-only EXCAP, will not discuss dyadic support or ways of dealing with stress.

6.7 ***Intervention contact and tracking***

6.7.1 A study team member will make phone or e-mail contact with participants each week to answer any questions they may have regarding the exercise program and to facilitate proper adherence

and compliance to the exercise intervention. In Arm 1, the team member will speak with both the cancer survivor and the caregiver together. In Arm 2, the study team member will speak with the cancer survivor alone.

- 6.7.2 Participants will also complete a daily diary throughout the intervention period recording mood/psychological distress (all study participants) and physical activity (those randomized to receive exercise only). (Note: The daily diary will take approximately 30 seconds to complete.)
- 6.7.3 All Walking and Progressive Resistance Exercises will be performed off-site from the University of Rochester Cancer Center in a home-based participant-selected environment.

6.8 *Post-intervention assessment*

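### The caregiver aim is a between-arm comparison, but the only caregiver test stated is a before-after t-test within EXCAP-PA, which cannot separate benefit from change common to both arms

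*Combined protocol and SAP*

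**What the plan says.** **The aim.** Section 2.5.1 sets out to estimate the effect of EXCAP-PA against survivor-only EXCAP "on self-reported psychological distress and biological endpoints associated with distress among caregivers". Section 13.2 lists the caregiver measures at the post-intervention visit: POMS total, cortisol, SAA and CRP, support received (DSQ) and actigraphy.

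**The test.** The first of the two paragraphs numbered 13.3.3 says: "We will also evaluate change in caregiver distress scores from baseline to post-intervention in the EXCAP-PA condition using paired sample t-tests". The stated purpose is "to examine whether caregivers benefit from supporting LGBT cancer survivors".

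**The other analyses.** The ANCOVAs in 13.3.1 and 13.3.2 belong to the primary and secondary aims, which are in survivors. The second 13.3.3 promises between-group comparisons for further outcomes. Its list contains neither POMS nor the biomarkers and does not mention caregivers.

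**The data.** Section 6.4.1 states: "All assessments will be done on all study participants (cancer survivors and their caregivers". Section 4.1 has caregivers in both arms assessed before and after the 6 weeks, with 35 randomised and 30 evaluable per arm.

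**The status of the results.** Section 4.1: "data collected from caregivers will be used for exploratory purposes only". Section 13.3.3: "Because of the many exploratory analyses involved, any results will only be used for hypothesis generation".

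**A separate matter, the diary.** Section 6.7.2 describes the daily diary as "recording mood/psychological distress (all study participants) and physical activity (those randomized to receive exercise only", and 10.2.1.2 agrees that everyone rates daily distress. The diary row of table 11.1 reads "Continuous (for those exercising".

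**The concern.** The aim is a contrast between randomised arms, and the stated test contains no contrast. It compares EXCAP-PA caregivers with themselves six weeks earlier and takes a fall in POMS as a sign of benefit. Anything that moves caregiver mood over that time, such as the calendar, completing the questionnaire again, or simply being in a study, enters the estimate at full weight.

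The design already supplies what is needed to remove it. Arm 2 caregivers are randomised with their survivors, told to keep their exercise unchanged, measured at the same two visits, and given the exercise kit only afterwards. The one stated caregiver test makes no use of them. The caregiver biomarkers, which are part of aim 2.5.1, have no named test at all.

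What is at stake is the caregiver hypothesis carried into the larger trial that 13.3.1 says this study should inform. An uncontrolled change could suggest a benefit that is not there, or hide one that is.

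**Working it through.** **Inputs.** SD of POMS total 13.01, baseline-to-post correlation r = 0.7, difference 6.90, level 0.05 (section 13.5.1, stated for survivors); two-sided test (13.3.1); 30 evaluable per arm (4.1). The documents give no caregiver SD, correlation or drift. The survivor SD and r are therefore an assumption here, and drift is shown as a range.

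**Step 1: reproduce the plan's own figure (survivors).**
- ANCOVA residual SD = 13.01 × √(1 − 0.7²) = 9.29.
- SE of the arm difference = 9.29 × √(2/30) = 2.40.
- Noncentrality = 6.90 / 2.40 = 2.88. With 57 df, power = 80.7%, which agrees with the stated 80%.

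The inputs are thus coherent for a baseline-adjusted ANCOVA with 30 per arm. (The effect size of 0.58 printed beside the 6.90 does not follow from them, since 6.90 / 13.01 = 0.53. It plays no part below.)

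**Step 2: the paired t-test in Arm 1, n = 30.**
- SD of change = 13.01 × √(2 × (1 − 0.7)) = 10.08.
- SE of mean change = 10.08 / √30 = 1.84.
- A mean fall of about 3.76 points is enough for two-sided significance (29 df).

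**Step 3: no intervention effect, the same fall in both arms.** The paired column uses the noncentral t with 29 df and noncentrality drift / 1.84. The ANCOVA column is a 40,000-run simulation with 30 per arm.

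| Common fall (points) | Paired t-test: significant improvement | Two-arm ANCOVA: significant benefit |
|---|---|---|
| 0 | 2.5% | 2.4% |
| 2 | 18% | 2.6% |
| 3 | 35% | 2.4% |
| 4 | 56% | 2.5% |
| 5 | 75% | 2.4% |

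The two-sided ANCOVA rate is 4.9% to 5.1% throughout.

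**Step 4: sensitivity to r.** At a 3-point fall, the paired test signals improvement in 23% of trials if r = 0.5 and in 49% if r = 0.8.

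**Step 5: the opposite direction.** With a true 5-point benefit and a 3-point worsening common to both arms, the paired test finds benefit in 18% of trials and the ANCOVA in 53%.

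**Step 6: what the ANCOVA costs in power.** With no drift, the paired test detects a true 5-point benefit in 75% of trials against 53% for the ANCOVA, and a 6.90-point benefit in 95% against 80%. The paired test's advantage comes from taking the drift to be exactly zero, which it cannot check. Its 75% is also what it returns when there is no benefit and a 5-point common fall.

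**The case against.** The strongest reply is about standing. Caregiver outcomes are the lowest tier of this trial: section 4.1 makes them exploratory and 13.3.3 confines the results to generating hypotheses. No primary or secondary conclusion, sample size or safety matter depends on the paired test. That stands, and it sets the severity. It does not make the test answer the aim.

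The second reply is that the sizes are hypothetical. No drift is given anywhere, and the SD and r are survivor values. Regression to the mean has no built-in source, because sections 3.3 to 3.5 select neither survivors nor caregivers on distress. A 5-point fall would be about 69% of the 7.24-point EXCAP effect over usual care reported in section 1.5 (5 / 7.24 = 0.69), so the upper rows of the table may be generous. This also stands. The table shows what a given drift would do and does not forecast one.

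Three stronger readings are tempting and are not supported:
- **That Arm 2 caregiver data are to be discarded.** No passage says so. The sentence about paired tests is worded as an addition, and the between-group list in the second 13.3.3 is not limited to survivors. What is missing is a stated between-arm model for caregiver POMS and biomarkers.
- **That drift will be reported as caregiver benefit.** It could be, if it exists, runs towards improvement, and the plan's own restriction is set aside.
- **That Arm 2 caregivers will lose their daily distress ratings.** Sections 6.7.2 and 10.2.1.2 both say that everyone records them. One short table row conflicts with that but does not settle it, and diary distress is not among the caregiver measures in 13.2.

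**Conclusion.** The point holds as a mismatch between aim and test. Aim 2.5.1 is a between-arm question about caregiver distress and biological endpoints. The only stated caregiver test is a within-arm change in distress, and nothing else in section 13 fills the gap. Under the survivor SD and r, the chance of a significant but spurious improvement rises from 2.5% with no drift to 18% at 2 points and 75% at 5, while the two-arm ANCOVA holds its level. These figures assume 30 EXCAP-PA caregivers with both visits and a drift shared by both arms. The mismatch itself needs no assumption. Severity is should-fix: the remedy is clear and nearly free, but the results are exploratory.

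**What to change.** For aim 2.5.1, state an ANCOVA of the caregiver's post-intervention value on arm and the caregiver's baseline value, using caregivers from both arms, and report the adjusted difference with its 95% CI. Apply it to POMS total, cortisol, SAA and CRP. For consistency with 13.2, apply it also to DSQ and actigraphy, which lie outside the wording of the aim. Keep the exploratory label. Keep the paired change in EXCAP-PA caregivers as description only, shown beside the same summary for Arm 2, and do not use it to judge whether caregivers benefit.

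Separately, reconcile the daily diary row of table 11.1 with 6.7.2 and 10.2.1.2, so that it is clear who completes the daily distress item.

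The cost is a few sentences in 13.3.3 and one table row. The model is the one already specified for survivors, and it needs no new visits, samples or participants.
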